2. STUDY OVERVIEW

2.1. Study Design

Study 021e is a Phase 3, international, multicenter, open-label, extension study of ataluren in patients with nmCF that have completed participation in the double-blind study PTC124-GD-021-CF (Study 021).

All eligible patients that completed participation in Study 021 will be enrolled into the study. Eligible subjects will receive oral ataluren administered 3 times per day (TID) at respective morning, midday, and evening doses of 10-, 10-, and 20-mg/kg for 96 weeks. The detailed schedule of assessments are displayed in Table 1.

Screening and baseline procedures are structured to avoid a gap in treatment between the double-blind study (PTC124-GD-021-CF) and this extension study. When possible, Screening/Baseline (Visit 1) for this extension study should occur on the same day as the End-of-Study visit for the double-blind study (PTC124-GD-021-CF). During the treatment period, study assessments will be performed at clinic visits at Week 12 and thereafter every 12 weeks until the end of the study.

Planned interim safety analyses will be conducted by an independent data monitoring committee (DMC). The first safety review will occur when ~ 100 patients have completed >=36 weeks of treatment. The second safety review will occur when ~ 100 patients have completed >=72 weeks of treatment.

The study will be terminated prematurely according to company's strategic decision on March 2, 2017. All subject who are on-going by then will be discontinued.

Table 1. Schedule of Events

| Study Period | Screening/B aseline | Treatment Period | | | | | | Post-Treatment | | |
|---|---------------------|------------------|----|----|----|----|----|----------------|-----------------------------|--------------------|
| Study Week (±7 days) | Day 1 | 12 | 24 | 36 | 48 | 60 | 72 | 84 | End of Tx/ Premature D/C 96 | 4 Weeks Post-Tx |
| Visit | 1 | 2 | 3 | 4 | 5 | 6 | 7 | 8 | 9 | 10 |
| Informed consent | X | | | | | | | | | |
| CFQ-R administration | X ^a | X | X | X | X | X | X | X | X | |
| Vital signs | Xa | X | X | X | X | X | X | X | X | X |
| Height | X ^a | X | X | X | X | X | X | X | X | X |
| Weight | X ^a | X | X | X | X | X | X | X | X | X |
| Physical examination | X ^a | | | | X | | | | X | X |
| Hematology | X ^a | X | X | X | X | X | X | X | X | X |
| Biochemistry | X ^a | X | X | X | X | X | X | X | X | X |
| Urinalysis | Xa | X | X | X | X | X | X | X | X | X |
| Renal ultrasound | Xa | | | | X | | | | X | |
| 12-lead ECG | X ^a | | | | X | | | | X | X |
| Study drug assignment | X | | | | | | | | | |
| Drug dispensed | X | X | X | X | X | X | X | X | | |
| Drug compliance | | X | X | X | X | X | X | X | X | |
| Adverse events | X | X | X | X | X | X | X | X | X | X |
| Concomitant medication | X | X | X | X | X | X | X | X | X | X |
| Spirometry | Xa | X | X | X | X | X | X | X | X | X |
| Respiratory event evaluation ^b | Xa | X | X | X | X | X | X | X | X | |
| P. aeruginosa in sputum | Xa | X | X | X | X | X | X | X | X | |
| Pharmacokinetics | | | Х | | X | | X | | X | |

^a Study procedure need not be performed if Day 1 is within 14 days of the end of study evaluations at Week 48 (Visit 8) of the preceding Phase 3 double-blind study (PTC124-GD-021-CF). If Day 1 is >14 days from the end of study visit, study procedure must be performed; however, it is not required to assess serum electrolytes, urine protein; urine creatinine ratio (spot sample), or urine blood (by dipstick).

^b Includes completion of the Respiratory Event Form.

^c **Abbreviations**: D/C = discontinuation; ECG = electrocardiogram; F/U = follow up; Tx = treatment

2.2. Study Objectives

2.2.1. **Primary Objective**

To evaluate the long-term safety of 10-, 10-, 20-mg/kg at luren in patients with nonsense mutation cystic fibrosis (nmCF), who previously participated in pivotal study PTC124-GD-021-CF, as determined by adverse events and laboratory abnormalities.

2.2.2. Secondary Objectives

The secondary objectives are:

- To evaluate the long-term effect of ataluren on pulmonary function
- To evaluate the long-term effect of ataluren on pulmonary exacerbation
- To determine the long-term effect of ataluren on medical interventions
- To evaluate the long-term effect of ataluren on HRQL
- To evaluate the long-term effect of ataluren on general well-being
- To assess long-term ataluren plasma exposure

2.3. Study Endpoints

2.3.1. **Primary Endpoint**

• Safety profile characterized by type, frequency, severity, timing, and relationship to ataluren of any adverse events, and laboratory abnormalities

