3.3. Clinical Endpoints

Primary

• Safety profile characterized by type, frequency, severity, timing, and relationship to ataluren of any adverse events or laboratory abnormalities

Secondary

- Changes in FEV₁, FVC, and FEF₂₅₋₇₅ as assessed by spirometry
- Rate, incidence, and duration of pulmonary exacerbations (modified Fuchs criteria)
- Incidences, rates, and durations of interventions (eg, antibiotic use and hospitalization) and disruptions to daily living (eg, missed school or work) resulting from pulmonary symptoms
- Changes in CFQ-R domains
- Changes in body weight and BMI
- New Pseudomonas aeruginosa lung infection
- Pre-dose ataluren plasma concentrations prior to morning ataluren administration at each clinic visit as assessed by a validated bioanalytical method
- Change from baseline in other safety parameters (eg, vital signs)

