14.1.4 Safety Profiling

As is conventional, safety will be characterized in terms of the type, incidence, timing, severity, drug-relatedness, and seriousness of adverse events and laboratory abnormalities. For consistency of interpretation, adverse events will be coded using the MedDRA, the severity of these events and laboratory abnormalities will be graded using the well-defined CTCAE, Version 3.0, and concomitant medications will be coded with the WHODRUG dictionary.

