4.10.1. Adverse Events

Adverse events will be classified by System Organ Class (SOC) and Preferred Term (PT) using the Medical Dictionary for Regulatory Activities (MedDRA Version 17.0). In order to remain consistent in the adverse event data collected in previous trials, the severity of adverse events will be graded by the investigator according to the CTCAE, Version 3.0 whenever possible. The adverse event CTCAE/severity grades include Grade 1 (Mild), Grade 2 (Moderate), Grade 3 (Severe), Grade 4 (Life-threatening), and Grade 5 (Fatal). The relationship of study drug to adverse event has 4 categories: probable, possible, unlikely and unrelated.

A treatment-emergent adverse event (TEAE) is defined as an adverse event that occurs or worsens in the period extending from the day of a subject's first dose of study drug to 4 weeks after the last dose of study drug in this study. In the following analyses, a subject having the

PTC Therapeutics, Inc. – Confidential Page 12 of 24 Version 1.0 14JUL2017 same event more than once will be counted only once. Adverse events will be summarized by worst CTCAE/severity grade.

Total numbers of AEs, TEAEs and serious AEs (SAE) and the number and percentage of subjects experiencing ≥1 TEAE, ≥1 SAE, discontinuation due to AE, and death will be tabulated. The number and percentage of subjects with TEAEs and SAEs will be by Relationship to study drug and CTCAE/severity, respectively.

The number and percentage of subjects experiencing a specific TEAE will be tabulated

- 1) by SOC, and PT
- 2) by SOC, PT, and CTCAE/severity grade
- 3) by SOC in the descending order of the SOC frequency in ataluren group,
- 4) by PT in the descending order of the PT frequency in ataluren group.

The following TEAEs will be analyzed similarly:

- 1) by SOC, and PT and
- 2) by SOC, PT, and CTCAE/severity grade.
 - Possibly or probably treatment-related TEAEs
 - Serious TEAEs and possibly or probably treatment-related serious TEAEs
 - TEAEs leading to discontinuation from treatment
 - Adrenal, hepatic and renal TEAEs and possibly or probably treatment-related adrenal, hepatic and renal TEAEs leading to special diagnosis evaluation
 - TEAEs with CTCAE/severity grade ≥3 and possibly or probably treatment-related TEAEs with CTCAE/severity grade ≥3
 - Common TEAEs (subject frequency of $\geq 5\%$)

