Listings of death, serious AEs, AEs leading to discontinuation from treatment, and adrenal, hepatic and renal AEs leading to special diagnostic evaluations will be provided. Renal AEs for subjects not using nephrotoxic concomitant medications, subjects using nephrotoxic concomitant medications, and subjects with postbaseline creatinine > 1.5*ULN will also be listed, separately.

The drug exposure adjusted TEAE incidence rate will be summarized by SOC and PT, where the incidence rate of the TEAE per 100 patient-year = (number of events/number of patient-years) *100. The number of patient-years is defined as the sum of the number of days on study drug of all patients divided by 365.25.

In addition, the number of subjects with clinical laboratory abnormalities, abnormal vital signs, and abnormal electrocardiogram reported as TEAE will be summarized.

Non-serious TEAE will be displayed by SOC and PT. The common non-serious TEAE (subject frequency of ≥5%) will also be displayed by SOC and PT.

Numbers of occurrence of serious TEAE and the numbers of occurrence of non-serious TEAE will be summarized by SOC and PT, separately.

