As necessary, laboratory abnormalities will be described by duration of study drug exposure, by dose, by age group, by sex, by race, by weight, and for special populations (eg, antibiotic use).

Table 2. Safety Monitoring Parameters and Actions To Be Taken

| Organ System and Laboratory Parameter | Stop Study Drug Immediately, Confirm Abnormal Value, and Then Start Work-Up ^a | Stop Study Drug After Confirming Abnormal Value, and Then Start Work-Up ^a | Continue Study Drug, Confirm Abnormal Value, and then Start Work-Up ^a | |
|--|---|--|--|--|
| Hepatic | | | | |
| Serum total bilirubin ^b | ≥Grade 3 (≥3.0 x ULN) | Grade 2 (1.5 – 3.0 x ULN) | | |
| Serum ALT | ≥Grade 3 (≥5.0 x ULN) | Grade 2 (>2.5 – 5.0 x ULN) | | |
| Serum AST | ≥Grade 3 (≥5.0 x ULN) | Grade 2 (>2.5 – 5.0 x ULN) | | |
| Serum GGT | ≥Grade 3 (≥5.0 x ULN) | Grade 2 (>2.5 – 5.0 x ULN) | | |
| Renal | | | | |
| Serum cystatin C | >2.00 mg/L | >1.33 – 2.00 mg/L | | |
| Serum creatinine | ≥ Grade 2 (≥1.5 x ULN for age) | Grade 1 (>ULN – 1.5 x ULN for age) | | |
| Serum BUN | ≥3.0 x ULN | ≥1.5 – 3.0 x ULN | | |

^a Laboratory abnormalities may be confirmed immediately or at the next scheduled clinic visit based on investigator judgment.

Abbreviations: ALT = alanine aminotransferase, AST = aspartate aminotransferase, BUN = blood urea nitrogen, GGT = gamma glutamyl transferase, ULN = upper limit of normal

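### Timing is a named part of the primary endpoint, but the SAP's adverse-event tables pool the whole study and cannot show whether risk is early, constant or late

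*SAP*

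**What the plan says.** Both documents make timing part of the primary endpoint. SAP 2.3.1 has "Safety profile characterized by type, frequency, severity, timing, and relationship to ataluren", for adverse events and laboratory abnormalities; Protocol 3.3 lists the same elements. Protocol 14.1.4 repeats the intention: "safety will be characterized in terms of the type, incidence, timing, severity, drug-relatedness, and seriousness of adverse events and laboratory abnormalities".

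SAP 4.10.1 then sets out the adverse-event summaries:

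- One TEAE window, from the first dose to "4 weeks after the last dose of study drug in this study", with no sub-periods.
- "The number and percentage of subjects experiencing a specific TEAE will be tabulated" by SOC and PT, and again with severity grade. Similar tables follow for related, serious, discontinuation-causing, adrenal/hepatic/renal, Grade 3 or higher and common TEAEs.
- Counts of occurrences of serious and non-serious TEAEs by SOC and PT.
- An exposure-adjusted rate by SOC and PT: "the incidence rate of the TEAE per 100 patient-year = (number of events/number of patient-years" × 100, where patient-years are all patients' days on drug added together.

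Laboratory data are treated differently. SAP 4.10.2 commits to summaries by visit and shift tables to each visit, and adds that, as necessary, "laboratory abnormalities will be described by duration of study drug exposure". SAP 4.12.1 has a matching sentence for vital signs. SAP 4.10.1 has none for adverse events.

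SAP section 6 lists the analyses changed because of early termination. The time-of-withdrawal analysis is among those removed. Adverse-event timing is not mentioned.

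**The concern.** The study exists to describe long-term safety. A reader of the report will want to know whether events cluster after the first dose, stay level, or rise with longer exposure. The planned adverse-event tables answer none of these, because each adds up the whole study.

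Two features of the design make this more than a formality. Patients come from both arms of Study 021, so Week 0 of 021e is first exposure for some and follows about 48 weeks of ataluren for others. SAP 4.11 splits FEV₁, FVC and exacerbations by preceding arm, but SAP 4.10.1 does not split adverse events. Follow-up is also cut at different lengths by the termination in SAP 2.1, so a pooled rate gives most weight to early exposure.

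The time pattern also bears on the protocol's own safety argument. Protocol 14.2.4 says transient creatinine elevations had no cumulative effect, and Protocol 15.3 says renal markers stabilised early in the nmDMD trials. A long-term extension is a natural place to examine the same pattern in reported renal events.

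**Working it through.** The documents give no figure on this point, so there is nothing to reproduce. The check sets the endpoint beside the tables, then uses assumed inputs to show what the tables can and cannot reveal.

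**1. Endpoint element against planned adverse-event summary (SAP 4.10.1)**

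| Element | Summary planned |
|---|---|
| Type | SOC and PT tables |
| Frequency | Subjects, occurrences, exposure-adjusted rate |
| Severity | Tables by worst grade |
| Relationship | Tables of possibly or probably related TEAEs |
| Timing | None; onset dates in listings only |

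**2. What one pooled rate can show**

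Formula (SAP 4.10.1): rate = events / (days on drug / 365.25) × 100. Assume 200 patients (Protocol 5.1 plans about 200), equal exposure for all, and 40 events (an invented count).

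- At 96 weeks each: 200 × 96 × 7 / 365.25 = 368.0 patient-years, so the pooled rate is 40 / 368.0 × 100 = 10.9.
- Any 12-week interval holds 200 × 84 / 365.25 = 46.0 patient-years.
- Even onset: 10.9 in weeks 0-12 and 10.9 afterwards.
- All onset in weeks 0-12: 40 / 46.0 × 100 = 87.0, then 0.
- All onset in the last 12 weeks: 0 until then, then 87.0.

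The planned table prints 10.9 in all three cases. At 72 or 48 weeks of exposure it would print 14.5 or 21.7, again whatever the pattern.

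**3. How uneven follow-up may be**

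Inputs: first dose in Study 021 on 15 August 2014, an estimated 14 months of recruitment and 48 weeks of treatment (Protocol section 1); termination on 2 March 2017 (SAP 2.1). Assumptions: uniform entry, immediate rollover, no dropout, treatment ending on that date.

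- Earliest 021e start: 15 August 2014 + 48 weeks = 17 July 2015. To 2 March 2017 is 594 days = 84.9 weeks.
- Recruitment span: 426 days = 60.9 weeks. Shortest follow-up: 84.9 − 60.9 = 24.0 weeks.
- Share passing Week 48: (84.9 − 48) / 60.9 = 61%.
- With 12 months of recruitment (365 days = 52.1 weeks): 36.9 / 52.1 = 71%.
- With 18 months (549 days = 78.4 weeks): 36.9 / 78.4 = 47%.

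Dropout before Week 48 lowers every figure.

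**4. Where the person-time lies (14-month case)**

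Mean follow-up is (24.0 + 84.9) / 2 = 54.4 weeks. Patients who pass Week 48 average 36.9 / 2 = 18.4 weeks beyond it, which over all patients is 0.606 × 18.4 = 11.2 weeks. So 11.2 / 54.4, roughly a fifth of exposure, lies beyond Week 48. A pooled rate therefore mostly reflects earlier exposure.

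**5. Two details that affect any analysis by onset**

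- Events count until 4 weeks after last dose, but the denominator counts only days on drug. For a patient with the average 18.4 weeks beyond Week 48, the extra 4 weeks lengthen the event period by 4 / 18.4 = 22% with no matching person-time.
- SAP 5.5.1 imputes partial start dates against the first dose of double-blind drug, although 021e is open-label. Take a patient first dosed in Study 021 on 15 August 2014 and in 021e on 17 July 2015, with an event dated only 2015. Read literally, the rule gives 1 January 2015, before 021e began. Anchored to 021e, it gives 17 July 2015.

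**The case against.** A reader might infer that early and late events cannot be told apart at all. The documents do not support that. Protocol 9.3 has onset and resolution dates recorded, SAP 4.1 plans by-subject listings for each CRF module, and SAP 4.10.1 adds dedicated listings of deaths, serious events, discontinuations, and adrenal, hepatic and renal events leading to special evaluation. What is missing is a summary. Listings show individual onsets but do not set them against the number of patients still being followed.

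A reader might also think that timing fails for the whole endpoint. It does not. The laboratory half is firmly covered by visit, and the hepatic and renal action thresholds in SAP Table 2 are all laboratory values.

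Nor does the pooled rate itself assume a constant hazard. Events over person-time is a valid average rate, and SAP 4.2 calls all analyses descriptive. Constancy is needed only if the figure is read as the risk at each point in time.

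Nor did the SAP drop a table that the protocol had planned: Protocol 11.4.5.1 contains no adverse-event timing summary either, and an endpoint characterised by timing is not an explicit promise of rates over time.

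Finally, the follow-up figures are soft. Recruitment was an estimate; expected Study 021 enrolment is about 208 in Protocol 11.1 and about 279 in SAP 2.4; Protocol 7.1.2 allows for rollover gaps of more than a month; and the March 2017 date could be that of the decision or of the end of treatment.

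All of this narrows the point. It leaves one element of the primary endpoint with no adverse-event summary and no stated reason.

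**Conclusion.** The point holds for the adverse-event summaries only. If the SAP is followed as written, its adverse-event tables cannot separate early, constant and late risk. That conclusion rests on the text and needs no assumption. The illustration gives its size: one pooled rate of 10.9 per 100 patient-years is compatible with a weeks 0-12 rate anywhere from 0 to 87.0, given an assumed 40 events in 200 patients followed for 96 weeks.

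The follow-up range of about 24 to 85 weeks and the 61% passing Week 48 depend on the assumptions in the working. The share runs from about 47% to 71% as recruitment goes from 18 to 12 months, and is lower with dropout. These figures show why the time pattern is worth tabulating; they are not statements about what happened. Nothing here suggests that a late or early risk exists. The change is worth making because the data are already collected and the endpoint names this element.

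**What to change.** Amend SAP 4.10.1 (SAP section 1 allows refinements before database lock):

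1. Add exposure-adjusted rates of TEAEs, serious TEAEs, and renal and hepatic TEAEs by onset interval since first 021e dose: 0-24, >24-48 and >48 weeks. Show the number of events and the person-time at risk in each interval, overall and by preceding Study 021 arm.
2. Use the same period for events and person-time. The simplest way is to run the denominator to 4 weeks after last dose, or to last contact if earlier, to match the TEAE window.
3. In SAP 5.5.1, anchor partial adverse-event start dates to the first dose in 021e.

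If the sponsor decides against the tables, section 6 should state that adverse-event timing will be shown only in listings.

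The cost is one extra table set and no new data. Late counts will be sparse. In the 14-month case with 200 patients, the average 24.0, 19.3 and 11.2 weeks per patient in the three intervals (54.4 − 24.0 − 11.2 = 19.3 rounded from unrounded values; 19.2 from those shown) give about 92, 74 and 43 patient-years on drug (weeks × 200 × 7 / 365.25). An event occurring at 10.9 per 100 patient-years would be expected about 43 × 0.109 = 4.7 times beyond Week 48, across both preceding arms. The tables should therefore be read descriptively, with no tests between intervals or arms.

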2.3.2. Secondary Endpoints

- Changes in FEV₁, FVC, and FEF₂₅₋₇₅ as assessed by spirometry
- Rate of pulmonary exacerbations (modified Fuchs criteria)

2.3.3. Tertiary Endpoints

- Change from baseline in other safety parameters (eg, vital signs, body weight, height, BMI, 12-lead ECG measurements, renal ultrasound)
- Incidence of new *Pseudomonas aeruginosa* lung infection
- Pre-dose ataluren plasma concentrations prior to morning ataluren administration at each clinic visit as assessed by a validated bioanalytical method

2.3.4. Other Endpoints

• Study drug extent of exposure and characterization of investigator-prescribed dosing modifications

• Study drug compliance as assessed by a subject daily diary and by quantification of used and unused study drug

• Incidence of concomitant therapies

2.4. Sample Size

The sample size for this extension study is not based upon any formal statistical hypothesis, but its upper bound is determined by the requirement that patients must have participated in the previous Phase 3 study of ataluren (PTC124-GD-021-CF) in which \sim 279 patients are expected to be enrolled.

3. STUDY POPULATIONS

3.1. As-Treated Population

The as-treated population consists of all subjects who took at least one dose of ataluren. This population will be used to analyze safety and treatment administration.

3.2. Intention-to-Treat (ITT) Population

The Intent-to-Treat (ITT) population consists of all as-treated subjects who have at least 1 post-baseline efficacy assessment. This population will be evaluated in the analysis of efficacy

4. STATISTICAL AND ANALYTICAL PROCEDURES

4.1. General Statistical Considerations

By-subject listings will be created for each CRF module. Summary tables for continuous variables will contain the following statistics: n, mean, standard deviation, standard error, and 95% confidence intervals (CIs) on the mean, median, minimum, and maximum. Summary tables for categorical variables will include N, n, percentage, and 95% CIs on the percentage. Where applicable, the summary data (mean, standard error) will be presented in graphical form by time of visit.

Unless otherwise specified, all applicable analyses will be 2-sided at the 0.05 level of significance.

All analyses and tabulations of data will be performed using SAS (Version 9.1 or higher).

4.2. Control of the Multiplicities

Since all analyses are descriptive in this study, there is no need to control the multiplicity.

4.3. Missing Data Handling

In general, the missing data in safety endpoints will not be imputed, unless specified otherwise. The imputation rules of missing start/stop dates in adverse events and prior/concomintant medications/therapies will be documented in Section 5.5.

4.4. Multiple Centers

Study centers from different countries will be pooled by geographic region (North America [US and Canada], Europe, and Other [ie, Australia, Israel, Argentina, and Brazil]). The number of subjects in each region will be reported.

4.5. Subject Disposition

4.5.1. Accounting for Subjects

Subject enrollment status will be summarized by country and site for the As-Treated population. The number and percentage of subjects will also be reported by all enrolled subjects, the ITT population, and the As-Treated population. The number of subjects at each scheduled visit will be tabulated for the As-Treated population. For the As-Treated population, the number of completers, subjects who discontinue prematurely from the study, and reasons of discontinuation will be tabulated. In addition, reasons of screening failures will be summarized and listed.

4.5.2. **Protocol Deviations**

All major protocol deviations will be summarized by type for the ITT population. A listing of major and minor protocol deviations will be provided.

